1.3. Temozolomide

Temozolomide is an oral alkylating agent. The benefit of temozolomide was demonstrated in a phase III trial of GBM patients randomized to post-operative involved field radiation (60 Gy in 2 Gy fractions) with or without concurrent and adjuvant temozolomide. The addition of temozolomide led to a significant improvement in overall survival (14.6 vs. 12.1 months)(4). The safety of radiation dose escalation up to 60 Gy in 3 Gy per fraction with concurrent temozolomide has been reported, with clinical outcomes similar to that of a conventional fractionation regimen. Only one patient in this study suffered a grade 3-4 nausea and vomiting during the adjuvant temozolomide administration(22). Chen and colleagues recently reported their phase I trial of hypofractionated intensity modulated radiotherapy (IMRT) with concurrent TMZ for primary treatment of GBM(23). Patients with a tumor up to 6 cm in size were treated with a 5 mm margin with escalating doses of IMRT, safely reaching 60 Gy in 10 fractions. Even with this extreme hypofractionation with concurrent chemotherapy, with potential tumor volumes up to 180 cm³ (6 cm tumor + 5 mm margin), no maximum tolerated dose was reached.

A 4-week course of hypofractionated intensity-modulated RT with concurrent and adjuvant temozolomide has been shown to be well tolerated, with eighty-three percent of the patients completing the combined modality treatment. Compared to conventionally fractionated RT, the hypofractionated course decreased the duration of RT treatment down to 4 weeks with comparable median overall survival rates(24).

Hypofractionated RT has been used with concurrent temozolomide in treatment of brain metastases and appears to be well tolerated, even when the entire brain is irradiated: Kouvaris *et al.* treated patients with brain metastases from solid tumors with whole brain radiation to a dose of 36 Gy in 3 Gy fractions with concurrent and adjuvant temozolomide and reported minimal side effects(25). Similarly, Hofman and colleagues showed that whole brain RT (20 Gy in 4 Gy fractions or 30 Gy in 3 Gy fractions) and stereotactic radiosurgery (20 Gy in a single fraction) with concurrent temozolomide were well tolerated(26).

Given the preclinical glioblastoma data demonstrating improved tumor control and decreased tumor cell repopulation with hypofractionated RT, a study of SRS in conjunction with temozolomide for treatment of GBM is warranted. The goal of this phase I study is to determine the maximum tolerated dose (MTD) of five fraction stereotactic radiosurgery with concurrent and adjuvant temozolomide for treatment of GBM.

3. PARTICIPANT SELECTION AND ENROLLMENT PROCEDURES

Refer to the Participant Eligibility Checklist in Appendix A.

3.1 Inclusion Criteria

- 3.1.1 Histopathologically confirmed newly diagnosed glioblastoma multiforme. Diagnosis must be made by surgical biopsy or excision.
- 3.1.2 The tumor must be supratentorial in location.
- 3.1.3 The planning target volume (PTV), defined as residual T1 post-contrast enhancing tumor and/or resection cavity plus 0.5 cm margin, must measure $\leq 150 \text{ cm}^3$ in volume. This volume will not be known at the initial consultation; it will be determined once the final radiation plan is completed.
- 3.1.4 Age ≥ 18 years.
- 3.1.5 Life expectancy of at least 12 weeks.
- 3.1.6 Patient must have adequate organ function as indicated by the following laboratory values:

System	Laboratory Value
Hematological	
Absolute neutrophil count (ANC)	$\geq 1,800 \text{ cells/mm}^3$
Platelets	$\geq 100,000 \text{ cells/mm}^3$
Hemoglobin	$\geq 8 \text{ g/dL}$. If anemia is present to the extent that the hemoglobin is $< 8 \text{ g/dL}$, then correction by transfusion is indicated before entry into the study.
Renal	
BUN	$\leq 30 \text{ mg/dL}$
Creatinine	≤ 1.7
Hepatic	
Serum total bilirubin	≤ 2.0
AST (SGOT) and ALT (SGPT)	$\leq 3 \text{ X ULN}$

- 3.1.8 Ability to understand and the willingness to sign a written informed consent document

3.2 Exclusion Criteria

- 3.2.1 Patients who have previously been treated with brain irradiation to the region that would result in overlap of the radiation fields.

- 3.2.2 Tumor foci detected below the tentorium.
- 3.2.3 Multifocal disease or leptomeningeal spread.
- 3.2.4 Prior allergic reaction to the study drugs involved in this protocol.
- 3.2.5 Inability to have neither an MRI nor a CT scan. Patients with a pacemaker must undergo CT instead of MRI to be eligible.
- 3.2.6 Pediatric patients (age <18), pregnant women, and nursing patients will be excluded.

3.3 **Informed Consent Process**

Patients who meet the inclusion and exclusion criteria who are seen in the neuro-oncology, neurosurgery, or radiation oncology clinic will be identified for recruitment. Patients will be evaluated by a multi-disciplinary team composed of radiation oncologists, neurosurgeons, and neuro-oncologists. During their visit, either a physician or a research coordinator will explain the study to the patient. They will be given the informed consent form to read. If they agree to participate, they will be asked to sign the consent form prior to participating.

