4. TREATMENT PLAN

4.1 Pretreatment evaluation

Patients will be evaluated by a multi-disciplinary team composed of radiation oncologists, neurosurgeons, and neuro-oncologists to assess for their eligibility. Patient's oncologic history, presenting symptoms, physical examination, pathology, and imaging studies will be reviewed. Patients will be evaluated for surgical candidacy and respectability.

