4.5.7. Recall blisters post-sun exposure can be treated with Domeboro soaks. If neuropathy occurs, patients may be placed on gabapentin.

4.5.8. No other chemotherapy treatment is permitted during protocol treatment.

4.6 **Duration of Therapy**

The first dose of temozolomide will begin the day before the first fraction of radiation. It will be taken through the day of the last fraction of radiation. Following radiotherapy, maintenance temozolomide will be prescribed at the discretion of the treating neuro-oncologist.

4.7 **Duration of Follow Up**

Patient follow-up schedule is summarized under section 8. Study Calendar.

The following will be obtained at pre-treatment evaluation and at each follow-up time points: Neurologic history and physical examination, KPS, steroid use assessment, and toxicity evaluation (see Follow-up assessment form). MRI with gadolinium will be obtained pre-treatment and at 1, 6, and 12 months following treatment until progression is documented.

In addition to the follow-up schedule outlined in section 8, additional clinical follow-up and MRI scans will be obtained based on clinical progress during the first 12 months following radiation.

After the first 12 months or after the documentation of disease progression, patients will be followed every 3-6 months at the discretion of the treating physician.

For those subjects who are unable to come for clinic visits, clinical follow-up information will be obtained via 1) a phone call to the patient and/or 2) clinic source document from his/her local physician. For patients unable to return to for imaging studies, source documents from outside institutions will be used to document imaging follow-up.

4.8 **Criteria for Removal from Study**

- Disease progression or death
- Intercurrent illness that prevents further administration of treatment: a condition, injury, or disease unrelated to cancer, that renders continuing temozolomide or radiation treatment unsafe or regular study visits impossible, including, but not limited to, active infection, symptomatic congestive heart failure, unstable angina pectoris, cardiac arrhythmia, pregnancy, or psychiatric illness that would limit compliance with study requirements.
- Unacceptable adverse event(s) (see adverse events)
- Patient decides to withdraw from the study
- General or specific changes in the patient's condition that render the patient ineligible for the study

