- Non-compliance with study medication or protocol-required evaluations and study visits
- Inability of subject to comply with study requirements
- Determination by the investigator that it is no longer safe for the subject to continue therapy
- Patients who inadvertently become pregnant
- At the discretion of the treating investigators

Subjects/patients may withdraw at any time or be dropped from the study at the discretion of the investigator should any untoward effects occur. In addition, a subject/patient may be withdrawn by the investigator if he/she violates the study plan or for administrative and/or other safety reasons. Any adverse experiences which are present at the time of discontinuation/withdrawal should be followed until resolution or stabilization.

Subjects who are discontinued from the study will still be followed for disease progression and survival.

If the reason for withdrawal from the trial is the death of the subject, the two options for categorizing withdrawal are either progressive disease or an adverse event (AE; more than one AE may be documented as a reason for withdrawal). Only one event will be captured as the cause of death. Note that death is an outcome and not an AE.

All trial treatment-related toxicities and SAEs must be followed up until resolution.

Subjects/patients who discontinue from the study for reasons unrelated to the study (e.g., personal reasons, or adverse events after registration but prior to receiving study therapy) may be replaced as required for the study to meet its objectives. The decision to remove a subject/patient and to replace dropouts will be made by the treating investigator. The replacement will generally receive the same treatment or

treatment sequence (as appropriate) as the allocation number replaced.

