8. STUDY CALENDAR

Parameters	Pre-Entry	1 month ^a	6 month ^e	12 month ^e
History/ Physical Exam	X	X	X	X
KPS	X	X	X	X
HRQOL ^b	X	X	X	X
Labs ^c	X			
Brain MRI or CT ^d	X	X	X	X
Steroid use Assessment	X	X	X	X
Toxicity Evaluation		X	X	X
	^a ± 7 days			

	
^b EORTC-QLQ C30 and BN-20, MDASI-BT
 
^c Laboratory tests: complete blood count, general chemistry panel, and comprehensive metabolic panel
 
^d MRI schedule may change as indicated should patient have clinical deterioration; CT instead of MRI is acceptable if patient has pacemaker.
 
^e ± 1 month

--	---

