BUN			≤ 30 mg/dL
Creatinine			≤ 1.7
Hepatic – From Comprehensive Metabolic Panel			
Serum total bilirubin			≤ 2.0
AST (SGOT) and ALT (SGPT)			≤ 3 X ULN

Exclusion Criteria (From IRB approved protocol)			
1. Has the patient been previously treated with brain irradiation to the region that would result in overlap of the radiation fields?			
2. Are tumor foci detected below the tentorium?			
3. Is there multifocal disease or leptomeningeal spread?			
4. Is there any documentation of prior allergic reaction to the study drugs involved in this protocol?			
5. Is the patient unable to undergo an MRI OR CT scan?			
6. Is the patient under age 18, pregnant, or nursing?			

If subject files must include supporting documentation to confirm subject eligibility. The method of confirmation can include, but is not limited to, laboratory test results, radiology test results, subject self-report, and medical record review.

IV. Statement of Eligibility

By signing this form of this trial I verify that this subject is [**eligible** / **ineligible**] for participation in the study. This study is approved by the Stanford Cancer Institute Scientific Review Committee, the Stanford IRB, and has finalized financial and contractual agreements as required by Stanford School of Medicine's Research Management Group.

Treating Physician Signature:	Date:
Printed Name:	

Secondary Reviewer Signature:	Date:
Printed Name:	

Study Coordinator Signature:	Date:
Printed Name:	

B. Participant Initial Evaluation and Follow-Up Forms:

**Protocol ID: Hypofractionated Radiotherapy for Treatment of GBM
Patient Initial Consult Form**

Date of visit: _____

Study Arm: #1: PTV <60mL #2: PTV 60-150mL

Pt deemed ineligible based on final PTV volume of: _____ mL

Dose Level: 25Gy 30Gy 35Gy 40Gy

Patient Number at this Dose Level: _____

	Done	If done:	Not Done
History/Physical Exam		Date of H/P: _____	
KPS Assessment		KPS: _____	

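### Pregnancy is an exclusion and a removal criterion, but no pregnancy test is required, so an unrecognised pregnancy could pass the entry checks

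*Combined protocol and SAP*

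**What the plan says.** **Exclusion at entry.** Section 3.2.6: "Pediatric patients (age <18), pregnant women, and nursing patients will be excluded". The synopsis carries the same exclusion, and exclusion item 6 of the Appendix A checklist asks: "Is the patient under age 18, pregnant, or nursing".

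**Removal.** Section 4.8 names pregnancy twice. It is among the intercurrent conditions ("cardiac arrhythmia, pregnancy, or psychiatric illness that would limit compliance with study requirements") and has a bullet of its own ("Patients who inadvertently become pregnant").

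**Tests and assessments.** The Study Calendar (Section 8) marks laboratory work at Pre-Entry only. Footnote c defines it: "Laboratory tests: complete blood count, general chemistry panel, and comprehensive metabolic panel". Section 3.1.6 says "Patient must have adequate organ function as indicated by the following laboratory values" and then lists blood counts and renal and hepatic values. Section 4.1 describes the pretreatment work-up: "Patient's oncologic history, presenting symptoms, physical examination, pathology, and imaging studies will be reviewed".

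**Proof of eligibility.** Appendix A requires supporting documents in the subject file and adds: "The method of confirmation can include, but is not limited to, laboratory test results, radiology test results, subject self-report, and medical record review".

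**The concern.** An exclusion protects participants only if some required step can find the people it is meant to keep out. Here the exclusion is stated three times, but no required step would find a pregnancy that the patient does not know about. Asking her cannot reveal it, and none of the listed laboratory tests is a pregnancy test.

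At stake is exposure of an unrecognised pregnancy to cranial radiation and to temozolomide, which Section 4.4 describes as acting through DNA alkylation. Entry is open from age 18 with no upper limit, so women of childbearing potential are eligible.

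The removal rule is no backstop for this exposure. Concurrent treatment runs from the day before the first of five fractions to the day of the last, and the first scheduled visit after Pre-Entry is at 1 month. No pregnancy test is scheduled at that visit or later.

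**Working it through.** The plan gives no figure to reproduce and no formula applies. The check is to read each place where a pregnancy test could be required and record what stands there.

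| Place | What it contains | Pregnancy test? |
|---|---|---|
| Section 3.1.6, organ-function table | ANC, platelets, hemoglobin, BUN, creatinine, bilirubin, AST/ALT | No |
| Section 3.2.6 | The exclusion, with no method of ascertainment | No |
| Section 4.1, pretreatment evaluation | History, symptoms, examination, pathology, imaging | No |
| Section 4.4, contraindications | Hypersensitivity only | No |
| Section 4.7, follow-up | Neurologic history and examination, KPS, steroid use, toxicity, MRI | No |
| Section 4.8, removal | Pregnancy named twice, with no method of detection | No |
| Section 8, calendar and footnote c | Three laboratory items, Pre-Entry only | No |
| Appendix A, laboratory table | The same seven rows as Section 3.1.6 | No |
| Appendix A, exclusion item 6 | One yes/no question covering age, pregnancy and nursing | No |
| Appendix B, consult and follow-up forms | KPS, quality of life, steroid dose, MRI, toxicity | No |

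**Count.** Statements excluding pregnancy at entry: 3 (synopsis, Section 3.2.6, checklist item 6). Statements making it a reason for removal: 2 (both in Section 4.8). Pregnancy tests required: 0.

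**Tracing one patient.** Take a woman with an unrecognised early pregnancy who meets all other criteria.

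1. Section 4.1 reviews her oncologic history, examination, pathology and imaging. No item there is directed at pregnancy.
2. The footnote c bloods are drawn and the seven checklist values are entered. None of them is a pregnancy test.
3. Item 6 is answered no on her own report, which Appendix A accepts.
4. She is recorded as eligible and starts temozolomide the day before the first fraction.

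No required step has failed. A monitor could not record the absent test as a deviation, because no test was called for.

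**The case against.** **A site may test anyway.** Appendix A requires supporting documentation and puts laboratory results first among the accepted forms. Self-report is one option in a general sentence that covers all criteria, not a rule written for pregnancy. This stands, and it limits the wording. A reader might infer that such a pregnancy would certainly pass, or that the exclusion cannot be applied at all. The documents do not support either reading: known pregnancies are excluded, and a site may test on its own initiative. The supported statement is that no test is required, so an unrecognised pregnancy could be missed.

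**The trial's statistics.** A reader might infer that removing a pregnant patient costs a cohort of three one of its DLT-evaluable members. The documents largely answer this. Sections 4.3 and 10.2 allow further enrolment until at least three patients are evaluable, and Section 4.8 allows replacement. Neither rule names pregnancy among its examples, but both aim to restore the cohort. Section 4.8 also keeps following adverse experiences present at withdrawal, so removal need not make a patient unevaluable.

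**How many are affected.** A reader might apply an assumed share of women of childbearing potential to the maximum of 30 patients (15 per arm × 2 arms). At an assumed 5% to 15% this gives 30 × 0.05 = 1.5 to 30 × 0.15 = 4.5 women. The share has no source in the documents, and the result counts women entering untested, not pregnancies. It does not measure the harm.

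**Other exclusions also lack a test.** Prior allergy (3.2.4) has none either. That is fair, so the case does not rest on comparison with the organ-function criteria. It rests on self-report being unable to reveal a condition the patient does not know she has.

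**Missing pages.** Consent and title pages are not in the supplied text, so a testing statement there cannot be ruled out. This carries limited weight, because the calendar and checklist, where a test would be scheduled and recorded, are present.

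**Conclusion.** The concern holds as a participant-safety gap in how eligibility is verified. Pregnancy is excluded at entry and is a reason for removal, yet no pregnancy test is required at any time in the supplied text. Followed exactly, the plan could expose an unrecognised pregnancy to radiation and temozolomide.

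The gap does not touch the 3+3 rules, the sample size, the DLT definition or inference on the MTD. The expected number of events cannot be estimated, because the documents give neither the age and sex mix nor a pregnancy rate. Such an event is probably rare, but its harm could be serious and irreversible, and the gap is cheap to close. The change should be made, but the trial's primary result does not depend on it.

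The conclusion assumes that the removed pages contain no testing requirement, and that sites do what the protocol requires and no more.

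**What to change.** Make Section 3.2.6, the calendar and the checklist agree:

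1. **Study Calendar, footnote c.** Add a pregnancy test for women of childbearing potential at Pre-Entry, on the existing blood draw, with the result available before the first protocol treatment. The timing needs stating because the Pre-Entry column has no window and Section 3.1.3 leaves final eligibility until the radiation plan is complete.
2. **Section 3.2.6.** Refer to that test as the means of confirming the pregnancy part of the exclusion.
3. **Appendix A, exclusion item 6.** Split it. Give pregnancy its own line with a result and date field, and a not-applicable option. Leave age and nursing to be confirmed as now, since a pregnancy test says nothing about nursing.

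This closes the gap at entry only. It adds no detection of pregnancies that arise later, so the removal bullet in Section 4.8 would still depend on the patient or clinician noticing.

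The cost is one inexpensive test for a few patients, one footnote, one cross-reference and one checklist line. No visit is added, and no dose or treatment rule changes.

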4. TREATMENT PLAN

4.1 Pretreatment evaluation

Patients will be evaluated by a multi-disciplinary team composed of radiation oncologists, neurosurgeons, and neuro-oncologists to assess for their eligibility. Patient's oncologic history, presenting symptoms, physical examination, pathology, and imaging studies will be reviewed. Patients will be evaluated for surgical candidacy and respectability.

4.2 Surgical treatment

Patients who are surgical candidates will undergo a surgical resection prior to radiotherapy. Patients whose tumors are unresectable or are not good surgical candidates will undergo a biopsy for tissue diagnosis.

4.3 Radiation Therapy

1.1.1. Dose specifications/escalation

Radiation will be delivered in five fractions. Provided that the MTD has not been reached, the total dose will be increased as follows:

Dose Level	Dose Per Fraction (Gy)	Total Dose (Gy)
1	5	25
2	6	30
3	7	35
4	8	40

There will be 2 arms to this study:

Arm	PTV volume (cm ³)
1	< 60
2	60-150

A minimum observation period of 30 days following radiotherapy is required prior to proceeding with the next higher dose level.

Common Terminology Criteria for Adverse Events (CTCAE) v4.0 will be used to grade adverse events:

(<http://evs.nci.nih.gov/ftp1/CTCAE/About.html>)

A dose limiting toxicity (DLT) is defined as a treatment related grade 3 - 5 CNS toxicity. Acute toxicity is defined as occurring within <30 days of the end of

radiotherapy. Late toxicity is defined as occurring ≥ 30 days of the end of radiotherapy. The highest dose achieved with an acceptable level of toxicity will be considered the MTD. The highest dose level allowed in this study is 40 Gy. The occurrence of late toxicities will be continuously monitored. If a late DLT occurs in 2 patients at a certain dose level after the radiation dose had already been escalated to the next level, the MTD will be backtracked to the level below the one at which the DLTs occurred.

Dose escalation will follow a traditional 3 + 3 design:

Number of Patients with DLT at a Given Dose Level	Escalation Decision Rule
0 out of 3	Enter 3 patients at the next dose level.
1 out of 3	Enter at least 3 more patients at the current dose level. 
 • If 0 of these 3 experiences a DLT (i.e., 1 out of 6), then proceed to next dose level. • If 1 or more of these 6 experiences a DLT (2 or more out of 6), then dose escalation will be stopped. Three additional patients will be entered at the next lower dose level if only 3 patients were previously entered.
>1 out of 3	Dose escalation will be stopped. Three additional patients will be entered at the next lower dose level if only 3 patients were previously entered.

Should a patient not be evaluable at 30 days (due to death unrelated to protocol treatment or loss to follow-up or discontinuation of the protocol follow-up per patient preference), then additional patients may be enrolled on each arm such that at least 3 are evaluable for DLT.

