1. OBJECTIVES

1.1.Phase I - Primary Objective

- 1.1.1 Determine the maximum tolerated dose (MTD), based on acute CNS toxicity at 30 days, of hypofractionated radiotherapy given in 5 fractions with temozolomide for the treatment of glioblastoma multiforme.

1.2.Secondary Objectives

- 1.2.1. Assess the short- and long-term adverse effects.
- 1.2.2. Determine the radiographic response rate.
- 1.2.3. Determine the overall survival rate.
- 1.2.4. Determine the patterns of tumor failure.
- 1.2.5. Assess quality of life during treatment.

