6. ADVERSE EVENTS AND REPORTING PROCEDURES

6.1 Potential Adverse Events

6.1.1. Radiation

6.1.1.1. Early, < 30 days from treatment: Expected adverse events include fatigue, alopecia, skin erythema, serous otitis, radiation pharyngitis, headache, neck pain, nausea and vomiting, and lethargy.

6.1.1.2. Late, > 30 days from treatment: Possible adverse events include focal neurologic deficits, memory difficulties, dementia, radiation necrosis, and radiation induced neoplasms.

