10. DATA REPORTING / REGULATORY CONSIDERATIONS

10.1 Monitoring plan

Stanford Cancer Center (SCC) Data and Safety Monitoring Committee (DSMC) will be responsible for monitoring the research yearly and will operate independently from the clinical investigators. The primary responsibility of the DSMC is to review the reported study data to confirm it is accurate, complete, and verifiable from source documents. The DSMC will also confirm that the conduct of the trial maintains the safety and well being of human subjects, and is in compliance with the currently approved protocol, with GCP, and with applicable regulatory requirements. Study

safety data will be reviewed by the DSMC in the form of summary reports or data listings on a regular basis.

10.2 Stopping rules (for the individual patient and for the study as a whole)

Dose escalation will follow a traditional 3 + 3 design.

Number of Patients with DLT at a Given Dose Level	Escalation Decision Rule
0 out of 3	Enter 3 patients at the next dose level.
1 out of 3	Enter at least 3 more patients at the current dose level. 
• If 0 of these 3 experiences a DLT (i.e., 1 out of 6), then proceed to next dose level.• If 1 or more of these 6 experiences a DLT (2 or more out of 6), then dose escalation will be stopped. Three additional patients will be entered at the next lower dose level if only 3 patients were previously entered.
>1 out of 3	Dose escalation will be stopped. Three additional patients will be entered at the next lower dose level if only 3 patients were previously entered.

Should a patient not be evaluable at 30 days (due to death unrelated to protocol treatment or loss to follow-up or discontinuation of the protocol follow-up per patient preference), then additional patients may be enrolled on each arm such that at least 3 are evaluable for DLT.

The occurrence of late toxicities will be continuously monitored. If a late DLT occurs in 2 patients at a certain dose level after the radiation dose had already been escalated to the next level, the MTD will be backtracked to the level below the one at which the DLTs occurred.

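### The late-DLT backtracking rule cannot fire at 40 Gy, and no other text clearly requires the MTD to drop after 2 late DLTs there

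*Combined protocol and SAP*

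**What the plan says.** Section 4.3 sets four levels (25, 30, 35 and 40 Gy in five fractions), escalated separately in two arms defined by target volume. It closes the scale at the top: "The highest dose level allowed in this study is 40 Gy".

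The terms that bear on late toxicity are these:

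- **DLT (4.3):** "A dose limiting toxicity (DLT) is defined as a treatment related grade 3 - 5 CNS toxicity". The definition carries no time window. Toxicity is then split into acute and late at 30 days after radiotherapy ends.
- **MTD (4.3):** "The highest dose achieved with an acceptable level of toxicity will be considered the MTD". No threshold is given for what is acceptable.
- **Late rule (4.3, repeated in 10.2):** if "a late DLT occurs in 2 patients at a certain dose level after the radiation dose had already been escalated to the next level", then "the MTD will be backtracked to the level below the one at which the DLTs occurred".
- **Primary objective (1.1.1):** the MTD is "based on acute CNS toxicity at 30 days".
- **Replacement of patients (4.3 and 10.2):** the sentence opens "Should a patient not be evaluable at 30 days", so evaluability for the 3+3 table is judged at that point.
- **Accrual (11.2.1):** at least 3 patients per level and 3 more at the MTD level, with a maximum of 15 per arm if all four levels are reached.

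Under late effects of radiation, 6.1.1.2 states: "Possible adverse events include focal neurologic deficits, memory difficulties, dementia, radiation necrosis, and radiation induced neoplasms". The study calendar has toxicity evaluations at 1, 6 and 12 months.

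**The concern.** The late rule shows that the sponsor regards 2 late DLTs at a level as enough to disqualify it. Its trigger depends on a higher level having been opened, so it lapses at the highest dose in the trial. The late events listed in 6.1.1.2 are ones that a 30-day window is not designed to capture.

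The MTD is the primary endpoint. Suppose an arm clears 40 Gy at 30 days and 2 of its 6 patients later have treatment-related grade 3-5 CNS toxicity. A reader who takes the 3+3 table as acute-only reports 40 Gy. A reader who counts late DLTs in the table reports 35 Gy. Both can cite the protocol, and the choice would be made after the data are known.

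**Working it through.** **1. The plan's own figure.** Four levels of 3 patients plus 3 more at the MTD: 4 × 3 + 3 = 15 per arm. This matches the synopsis and 11.2.1. It also gives the number at 40 Gy if that is the MTD: 3 + 3 = 6.

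**2. Can the late rule fire at each level?** It needs 2 patients with a late DLT and a next level already opened.

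| Level | Next level | Can fire? | MTD moves to |
|---|---|---|---|
| 25 Gy | 30 Gy | yes | no lower level exists |
| 30 Gy | 35 Gy | yes | 25 Gy |
| 35 Gy | 40 Gy | yes | 30 Gy |
| 40 Gy | none | never | (would be 35 Gy) |

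The same condition blocks the rule at any lower level where no higher dose was ever given. If the table stopped escalation there for acute DLTs, the MTD already lies lower. The gap would then matter mainly in an arm that closed early. At 40 Gy it is built into the design.

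**3. Does other text fill the gap at 40 Gy?**

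- *The 3+3 table.* For counting late DLTs: the DLT definition has no window and the late rule itself uses the term late DLT. Against: 1.1.1 specifies acute toxicity at 30 days, evaluability is set at 30 days, and late DLTs have their own rule.
- *The MTD definition.* It is not confined to acute events, but it states no number, so it permits a drop without requiring one.
- *Monitoring.* Late toxicities are watched continuously and a committee reviews safety (10.1), but neither provision contains a late-toxicity criterion for the MTD.

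None of these clearly requires 35 Gy, and none clearly forbids it.

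**4. How often would the case arise?** With n patients observed and late-DLT rate p, P(2 or more) = 1 − (1−p)^n − n·p·(1−p)^(n−1). For n = 6:

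- p = 0.10: 1 − 0.5314 − 0.3543 = 0.114
- p = 0.20: 1 − 0.2621 − 0.3932 = 0.345

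| Assumed late rate | 6 observed | 4 observed | 3 observed |
|---|---|---|---|
| 10% | 0.114 | 0.052 | 0.028 |
| 15% | 0.224 | 0.110 | 0.061 |
| 20% | 0.345 | 0.181 | 0.104 |
| 30% | 0.580 | 0.348 | 0.216 |

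The rates are assumptions. The column for 4 illustrates the loss of two patients to early death or progression. The column for 3 applies to a level that was not expanded. Under the present wording, the chance that the explicit rule acts at 40 Gy is 0 in every row.

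The background does not settle the rate. In one series (50 Gy in 5 Gy fractions, no chemotherapy), 3 of 20 were re-excised for necrosis, which is not this protocol's DLT. Another (60 Gy in 10 fractions with temozolomide) reached no MTD, and no late rate is reported for it.

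**5. Patients if the MTD backtracks from 40 to 35 Gy.** With 6 treated at 40 Gy and 35 Gy then expanded under 11.2.1: 3 + 3 + 6 + 6 = 18 per arm. Without expansion: 3 + 3 + 3 + 6 = 15, and the 35 Gy MTD rests on 3 patients.

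**The case against.** The best defence is that there is no gap. A late DLT is a DLT, the table counts patients with a DLT and names no window, and the prior-escalation condition simply divides the work: the table before escalation, the backtracking rule after it. On that view 2 DLTs at 40 Gy are more than 1 of 3, or 2 of 6, and 35 Gy follows. The acute-only reading also has a cost, since it leaves late DLTs that arise before escalation without a rule at any level. This reading is tenable, and it means the protocol cannot be said to lack any route to 35 Gy. But it sits badly with the 30-day basis in 1.1.1, so the ambiguity stands.

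It can also be said that no escalation decision depends on this, because nothing lies above 40 Gy; that an arm must first clear 40 Gy; and that late toxicity will be reported as a secondary endpoint anyway. All true. These limit the consequence to the dose that is named as the MTD, but that is the primary endpoint.

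A reader might infer that late toxicity goes unobserved after progression, because 4.8 removes progressing patients and mentions later follow-up for progression and survival. The documents do not support that. Section 4.7 continues follow-up every 3-6 months after progression, at the physician's discretion, and 4.8 requires treatment-related toxicities to be followed to resolution.

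**Conclusion.** The point holds in limited form and should be fixed. It is certain that the explicit late rule cannot fire at 40 Gy. It is a matter of reading, and so less certain, that nothing else compels a drop: the table might, but the primary objective and the evaluability rule point the other way.

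If an arm clears 40 Gy and all 6 patients are observed for late effects, the disputed case arises with probability 11% at an assumed late rate of 10%, 34% at 20% and 58% at 30%. With 4 observed, these fall to 5%, 18% and 35%. A reader might take such figures as the chance that this trial names the wrong MTD. They are not: they are conditional on clearing 40 Gy and rest on assumed rates, and the investigators could still choose 35 Gy by judgment.

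**What to change.** - **4.3 and 10.2:** delete the condition on prior escalation, so that 2 or more patients with a late DLT at 30, 35 or 40 Gy move the MTD down one level. The same deletion covers lower levels where no higher dose was given.
- **1.1.1:** say that the 30-day MTD is subject to this rule.
- **Mixed case:** say whether one acute plus one late DLT, in different patients at the same level, counts as 2. Otherwise the same disagreement remains.
- **Counting:** take late DLTs from all existing follow-up, including visits after progression under 4.7. Do not stop counting when a patient is removed from study.
- **Patients after backtracking:** if the level below has only 3 patients, either apply 11.2.1 and add 3, restating the maximum in the synopsis and 11.2.1 as 18 per arm on the 3 + 3 + 6 + 6 path, or state openly that the backtracked MTD rests on 3 patients.

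The cost is mostly wording. No new visits are needed, and escalation is not slowed by late follow-up at 40 Gy, because it is the last level. The first patient option adds 3 per arm on that path (18 − 15), or 6 if both arms take it.

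The downside is that the rule will sometimes reject an acceptable dose. With 6 observed at 40 Gy and a true late rate of 10%, it fires in about 11% of such arms, against 3% at a level with 3 patients, so a fixed count of 2 is stricter where more are treated. It fires less often if early death or progression limits observation. The sponsor should accept that trade knowingly.
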